[figure not shown]
## **THE EFFECT OF MUSIC DURING NON-STRESS TESTING ON WOMEN'S COMFORT, VITAL SIGNS AND ANXIETY: A RANDOMIZED CONTROLLED STUDY**

Music has direct and indirect positive effects on the mother and fetus during pregnancy and perinatal period. This study was aimed at investigating effects of music played during the Non-Stress Test (NST) procedure on the mother's comfort, vital signs and anxiety.

The present study is a randomized controlled experimental study. Pregnant women who presented to the NST outpatient clinic of a research hospital in the Central Anatolia region of Türkiye between June 2025 and August 2025 comprised the population of the study. The study's sample size was calculated using the G\*Power 3.1.9.2 software based on data from a study by Baskurt and Yilmaz [1]. The mean anxiety scores and standard deviation values from that study were used, and the effect size was calculated as 0.79. The minimum number of pregnant women to be included in the sample of this study was calculated as 70 pregnant women, 35 in each group, using the G\*Power 3.1.9.2 software, based on an effect size of 0.79, an alpha value of 0.05, and a power value of 0.95. To increase the analysis power of the study, the study sample consisted of 173 pregnant women (music group= 93 and control group= 80).

The inclusion criteria of the study were as follows: being between the ages of 18 and 45 years, having completed the 32nd week of gestation, not having any risk factors in their pregnancy (such as premature rupture of membranes, preeclampsia, gestational diabetes), not having multiple pregnancies, not having low (80/60 mmHg and below) or high (140/90 mmHg) blood pressure levels, having eaten at least two hours before the NST procedure, not smoking or consuming alcohol at least two hours before the NST procedure, being able to communicate, not having any hearing problems, and volunteering to participate in the study.

The exclusion criteria of the study were as follows: Pregnant women who had a fetus with fetal distress, for whom emergency intervention was considered by the physician, who had impaired NST and required immediate intervention, who had a psychiatric disease diagnosis and hearing impairment were not included in the study (Figure 1).

**Figure 1.** CONSORT flowchart

### ***Procedure***

*Selection of music:* The music played to the pregnant women was selected by the researchers in accordance with the definition of relaxing music made in the literature. Before the music selection, the researchers communicated with the TÜMATA (Turkish acronym for the "Research and Promotion of Turkish Music Association). After the meeting held with the association, it was decided to use the 'Acemasheran' (a musical mode in traditional Turkish music). In the study, music prepared by the TÜMATA in the Acemasheran mode was played. It is stated that Acemasheran mode helps balance the body, helps the listener relax, facilitates birth, helps correct the wrong position of the fetus in the womb, and has a pain and spasm relieving effect [2,3].

### *Randomization:*

Simple randomization method was used in this study. Pregnant women who met the study criteria were randomly assigned to the music or control group with equal probability, independently of any previous assignments, on the day they came to the hospital for their physical examination. The total number of pregnant women determined by the G\*Power analysis was entered into the program at "<https://www.randomizer.org/>," and randomization was conducted using the program. The assignment of the groups was performed on the computer, and the pregnant women were randomly assigned to the music and control groups.

### *Data collection:*

The data of the study were collected from the pregnant women using the face-to-face interview technique at the NST outpatient clinic on the days and hours when the researcher was present in the hospital. The participating pregnant women were not informed of the group they belonged to. Since only the researcher knew the participants' groups, single-blindness was achieved in the study.

*Music Group:* The purpose of the study was explained to the pregnant women who met the inclusion criteria. After their written consent was obtained, they were administered the Personal Information Form, Prenatal Comfort Scale, Vital Signs Form, and State Anxiety Scale used to measure their anxiety level before the NST procedure. They were asked to lie on their left or right side. After the pregnant women were positioned, while the NST procedure was implemented they listened to music for 20-30 minutes. The pregnant women listened to the music on an MP3 player during the application. The duration of the music recorded on the

MP3 player was 30 minutes. To avoid hygiene problems, each pregnant woman was provided with individual headphones, which were given to them as a gift after the procedure. The volume of the music was adjusted by the pregnant women. After the procedure was completed, the Prenatal Comfort Scale, Vital Signs Form and State Anxiety Scale were administered again.

*Control Group:* The purpose of the study was explained to pregnant women who met the inclusion criteria. After their written consent was obtained, they were administered the Personal Information Form, Prenatal Comfort Scale, Vital Signs Form, and State Anxiety Scale used to measure their anxiety level before NST. They were asked to lie on their left or right side. They underwent no other intervention during the NST procedure. After the procedure was completed, the Prenatal Comfort Scale, Vital Signs Form and State Anxiety Scale were administered again.

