### ***Data Collection Tools***

*Personal Information Form:* The form was administered to determine the participant's socio-demographic characteristics such as age, education level, employment status, family type, income level, and her obstetric characteristics such as whether her pregnancy was planned, what her gestational age was and whether she had undergone NST before.

*Prenatal Comfort Scale (PCS):* Takeishi et al. developed the PCS to determine the prenatal comfort level of the woman in Japan in 2011 [4]. In the first version, the PCS had 34 items, but then they revised it and shortened to 15 items [5]. The short version of the PCS consists of 15 items and the following 5 subscales: "The impact of developing relations with the spouse on the paternity role - Husband" (3,4,7,9), "Interacting with the movements of the fetus - Fetus" (13,14), "Social support received from the people around - People" (11,12,15), "Acceptance of the maternal role and attachment to the baby-Mother" (1,5,8), "Realizing the changes in oneself during pregnancy-Myself" (2,6,10). Response given to the items are rated on a six-point Likert type scale ranging from 0 to 5 (0 = Strongly disagree, 1 = Disagree, 2 = Undecided, 3 = Somewhat agree, 4 = Agree, 5 = Strongly agree). The minimum and maximum possible scores that can be obtained from the PCS are 0 and 75, respectively. The higher the score is the higher the comfort level is. Şenol, Özkan and Aslan performed the validity and reliability study of the Turkish version of the PCS (2020), the Cronbach's alpha value of the PCS was 0.815 in Şenol, Özkan and Aslan's study [6].

*Vital Signs Form:* The form was used to record the pregnant women's body temperature, pulse rate, respiration rate and blood pressure values.

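### The after-NST anxiety and comfort scores were most likely obtained by an interviewer who knew the allocation, and the claimed single-blinding does not protect them

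*Combined protocol and SAP*

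**What the plan says.** Three statements under Data collection in the combined protocol and SAP bear on this point.

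- **Mode:** "The data of the study were collected from the pregnant women using the face-to-face interview technique at the NST outpatient clinic". Collection took place "on the days and hours when the researcher was present in the hospital".
- **Blinding:** "The participating pregnant women were not informed of the group they belonged to", followed by "Since only the researcher knew the participants' groups, single-blindness was achieved in the study".
- **Outcome measurement:** in each arm, "After the procedure was completed, the Prenatal Comfort Scale, Vital Signs Form and State Anxiety Scale were administered again". The sentence is passive and does not say who did this.

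Under Data Collection Tools, the PCS is a set of self-rated items scored 0 to 5 and the SAS a set of self-rated items scored 1 to 4. Both ask about the woman's own state. No section mentions self-completion, a second assessor, sealed forms, or keeping the delivery of music apart from the collection of outcomes.

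**The concern.** The plan treats the fact that only the researcher knew the groups as its safeguard. For outcome measurement it is the weak point: the one person stated to know the allocation is also the only data collector mentioned, and the stated technique is an interview.

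Tone of voice, prompting, the handling of a hesitant answer and the way it is recorded can all differ between a woman known to have heard music and one known not to have. The plausible direction is lower SAS and higher PCS in the music arm, which is the result the study looks for. The Mann-Whitney and Wilcoxon tests in Statistical Analysis of the Data cannot separate such a shift from an effect of music. Anxiety is the outcome on which the sample size was based, and comfort is in the study title.

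This is a different matter from whether women hearing music can be blinded. That is largely unavoidable. Both instruments use fixed response options and do not need an interviewer, so this route to bias is avoidable.

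**Working it through.** **Who collected the outcomes**

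1. The interview sentence covers the study data as a whole and makes no exception for the after-NST scales.
2. Collection was tied to the presence of one researcher, in the singular.
3. That researcher knew the groups and, according to the text, nobody else did.
4. The after-NST sentence names no administrator, and no other assessor appears anywhere.

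Items 1 to 3 point to an interviewer aware of allocation. Item 4 makes this a strong inference and not a stated fact.

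**How much a bias could matter**

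The plan has no figure of its own to reproduce here: it gives no bias size and no SD. The following is a sensitivity calculation.

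Inputs:
- Arm sizes 93 (music) and 80 (control), from the sample-size paragraph.
- Significance level 0.05, from Statistical Analysis of the Data; the test is taken as two-sided (assumption, since sidedness is not stated).
- True effect of music zero (assumption).
- Shift between arms in the after-NST score, in favour of music, of b = 0.1, 0.2 or 0.3 SD (assumption).
- A two-sample t-test, as an approximation to the planned Mann-Whitney test.

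Formulas:
- Degrees of freedom = 93 + 80 − 2 = 171, with critical value 1.974.
- Noncentrality = b × √(93 × 80 / 173) = 6.558 × b.
- Chance of a significant benefit = P(noncentral t > 1.974).

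| b (SD) | Noncentrality | Significant in favour of music | Significant in either direction |
|---|---|---|---|
| 0 | 0 | 2.5% | 5.0% |
| 0.1 | 0.656 | 9.5% | 10.0% |
| 0.2 | 1.312 | 25.6% | 25.7% |
| 0.3 | 1.967 | 49.9% | 49.9% |

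For a claim of benefit the comparator is 2.5%, because half of the two-sided 5% lies in the other direction.

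The smallest observed difference that reaches p<0.05 is 1.974 × √(1/93 + 1/80) = 1.974 × 0.1525 = 0.30 SD. At the calculated minimum of 35 per group, the either-direction figures for the same shifts are 7%, 13% and 24%. Raising the sample to 173 therefore gives no protection. It makes a false positive from this source more likely.

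**The case against.** The strongest reply is that the text does not establish the mechanism. It does not say who gave the after-NST scales, whether items were read aloud, or who started the music. A face-to-face technique could include handing a woman a form in person. The same technique was used in both arms and at both times, so part of any interviewer influence would be common to the arms and cancel. The shifts of 0.1 to 0.3 SD have no source in the documents. All of this stands, and it is why the administrator is called likely and the magnitude conditional. It does not remove the point, because the plan describes no safeguard and relies on a blinding statement that leaves the data collector unblinded.

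Three stronger readings are tempting, and the documents do not support them.

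- **That self-completion would remove the bias at no cost.** Every woman was told the purpose of the study, and women in the music arm heard music through headphones that they kept as a gift. Their own expectations, and some wish to please, would remain whoever marked the form. There would also be skipped items and some assisted forms. The entry criterion of being able to communicate does not establish literacy.
- **That every outcome is biased, vital signs included.** Of vital signs the plan says only that "The form was used to record the pregnant women's body temperature, pulse rate, respiration rate and blood pressure values". It names neither device nor operator, and spoken prompting is not an evident route to error in an instrument reading. No claim is made here about vital signs.
- **That the text shows the person who delivered the music then questioned the woman aloud.** This may have happened, but it is not written.

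**Conclusion.** The concern holds for the SAS and PCS. As described, these subjective outcomes were most likely collected by an interviewer who knew the allocation, and the single-blinding described does not shield them from interviewer prompting or recording.

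On the stated assumptions, modest shifts would raise the chance of a false significant benefit from 2.5% to about 10%, 26% or 50%. These figures show sensitivity. They do not estimate the bias that occurred, and nothing in the documents shows that any did. The conclusion rests on reading the interview sentence as covering the after-NST scales. A clear statement that women completed the forms unobserved, or that someone unaware of allocation collected them, would largely answer it.

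**What to change.** State in Data collection who gave the SAS and PCS before and after NST, in what mode, and whether that person knew the allocation.

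If collection can still be changed, then in both arms and at both times have each woman complete the SAS and PCS on paper out of the researcher's view and seal them before the researcher sees the answers. Read items aloud only to women who cannot read, and flag those forms. This needs envelopes and a short procedural change, with no extra assessor. The price is some skipped items and some assisted forms. It reduces interviewer bias but does not blind the women.

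The document is written in the past tense with final arm sizes, so this may come too late. In that case, state in the conclusion that the SAS and PCS were obtained by an interviewer who knew the allocation (if the investigators confirm this), and do not present single-blinding as protection for these two outcomes. That costs a sentence or two of text.

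### The plan says single-blindness was achieved, but women in the music group knew what they had received when they gave the post-procedure anxiety and comfort ratings

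*Combined protocol and SAP*

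**What the plan says.** All the relevant statements are in the Data collection section of the combined protocol and SAP.

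- **The claim and its basis.** "The participating pregnant women were not informed of the group they belonged to". The next sentence gives the reason, "Since only the researcher knew the" participants' groups, and concludes that "single-blindness was achieved in the study".
- **Music group.** After the baseline forms and positioning, "while the NST procedure was implemented they listened to music for 20-30 minutes". The music came from an MP3 player, "each pregnant woman was provided with individual headphones" (kept as a gift), and "The volume of the music was adjusted by the pregnant women". The PCS, vital signs and SAS were then taken again.
- **Control group.** "The purpose of the study was explained to pregnant women who met the inclusion criteria", baseline forms were completed, and the women were positioned in the same way. "They underwent no other intervention during the NST procedure". The same three instruments were repeated afterwards.
- **Who collected the data.** Collection was by face-to-face interview, at times when the researcher was on site.

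The sample-size paragraph in the opening section gives 93 women in the music group and 80 in the control group. Under Data Collection Tools, the PCS is scored from the woman's agreement with each item (0 to 5), and the SAS from her grading of her own feelings (1 to 4).

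**The concern.** A single-blind label, with the researcher aware of allocation, tells the reader that the participants did not know which condition they were in. The plan supports it only by saying that the group was not disclosed to them. Withholding a group name does not conceal a treatment that the woman hears, wears and adjusts herself.

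The study title names comfort, vital signs and anxiety as outcomes. Comfort and anxiety are the women's own ratings. When a respondent knows what she has been given, such ratings can move with her expectations or her wish to oblige, apart from any effect of the music. If the interviewer also knows the allocation, there is a second route for influence. A reader who accepts the label will assume a protection for the SAS and PCS results that the described procedure does not provide. The two scales need not be equally exposed, and this point makes no claim about vital signs.

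**Working it through.** No formula lies behind the blinding claim, so the check follows the Data collection section in time order and asks who knew what at each step.

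| Step | Music group | Control group | Researcher |
|---|---|---|---|
| Baseline PCS, vital signs, SAS | Not told group; no music played yet | Not told group | Knew the groups |
| During the non-stress test | Music for 20-30 minutes, own headphones, own volume setting | No other intervention; no silent headphones or other audio described | Knew the groups |
| Post-procedure PCS, vital signs, SAS | Knows she has just heard music | Not stated whether she could infer her allocation | Knew the groups |

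**Baseline.** Nothing described here reveals the allocation to the women. Withholding the group could have served a purpose at this step.

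**Post-procedure, music group.** That the woman knows what she received follows directly from the procedure and needs no outside assumption.

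**Post-procedure, control group.** The purpose of the study was explained, but the text does not say how much of the music comparison was disclosed. That wording may be on consent pages not available for this review. Awareness among controls is therefore an open question.

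**Assessment.** The plan describes face-to-face interviews and a researcher who knew the groups. It does not say who administered each scale, and it describes no separate assessor kept unaware of allocation.

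**Numbers affected**, from the sample-size paragraph:

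- Total: 93 + 80 = 173, which agrees with the stated sample.
- Women for whom the claim fails at the post-procedure ratings: 93/173 = 53.8%.
- Women for whom it cannot be settled from the text: 80/173 = 46.2%.

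**The case against.** **The label may have meant only that group names were withheld, and the plan says so openly.** The basis for the label is stated, and the headphones and untreated control are described in the following paragraphs, so a careful reader can see the limit. Withholding the group may also have protected the baseline answers. That part stands, and the correction should not deny it. It does not rescue the claim, which is made without qualification although the ratings that follow the intervention are the ones given after the women have heard the music.

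**Music cannot be masked, so its absence is no defect.** Agreed. The fault is in saying that blinding was achieved. The choice of an audible intervention is not in question.

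**A reader might infer that no participant was blinded at any point.** The document does not support this. Control-group awareness is not stated, and the baseline scales came before any music.

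**A reader might try to size the problem by the smallest group difference that would reach significance at 93 versus 80.** That threshold would be the same under perfect blinding and for any other source of bias, so it does not measure this problem. The document gives no figure from which the size or direction of a reporting bias could be derived.

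**It is only wording.** True: no estimate, test or sample size is shown to be wrong. The sentence still misstates a main design feature that governs how two of the three outcome domains are read.

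**Conclusion.** The point holds for the post-procedure self-reported outcomes. The stated single-blindness is contradicted by the procedure in the same section for the 93 music-group women (53.8% of 173). For the 80 controls (46.2%) there was no sham, and whether they were aware of their allocation is unknown from the text. The researcher was not blinded, and no blinded assessor is described.

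For the music group, the conclusion assumes only that a woman who listens to music and sets its volume knows that she has done so. It does not extend to the baseline ratings. It also does not show that the SAS or PCS results are biased, only that the design leaves them open to bias that the label says was guarded against.

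**What to change.** 1. Replace the single-blind sentence in Data collection with, for example: *Participants were not told their group, but women in the music group could not be blinded to the music once it was played, control women had no sham, and the researcher knew the allocation; post-procedure outcomes were therefore not assessed blind.*
2. Add a statement that the post-procedure SAS and PCS results are open to reporting bias and to interviewer influence, and should be interpreted with that limit.

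The cost is a few sentences, and the trial loses the single-blind label. No change to data collection or analysis is needed, so the correction can be made even if recruitment (June to August 2025) has finished.

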### ***Statistical Analysis of the Data***

The data obtained in the present study were analyzed using the SPSS (Statistical Package for Social Sciences) 25.0. In the analysis of the data, to compare the homogeneity between the groups, cross tables were created for categorical variables, and the Chi square ( $\chi^2$ ) and Fisher's exact test were used. Numerical variables were given as mean $\pm$ standard deviation ( $X \pm SD$ ) whereas categorical variables were given as number (n) and percentage (%). For non-parametric data that were not normally distributed, the Mann-Whitney U test was used to evaluate the difference between two groups, and the Kruskal-Wallis H test was used to find differences between the variables with three or more categories. Spearman correlation analysis was performed to reveal the relationship between the dependent variables. The Wilcoxon test (significance test of the difference between two paired groups) was used to test the difference in the dependent groups at two different measurement times. The significance level was accepted as  $p<0.05$ . The confidence interval was 95%.

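### The within-arm before-after test on vital signs mixes any music effect with rest, elapsed time and possibly posture, and the plan does not say that the between-arm comparison decides

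*Combined protocol and SAP*

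**What the plan says.** The *Data collection* section gives the same order of events in each arm. After consent, women in the music arm complete the Personal Information Form and the "Prenatal Comfort Scale, Vital Signs Form, and State Anxiety Scale used to measure their anxiety level before the NST procedure"; the control paragraph lists the same forms at the same point. The next sentence in both paragraphs is "They were asked to lie on their left or right side".

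The arms then differ. For the music arm, "After the pregnant women were positioned, while the NST procedure was implemented they listened to music for 20-30 minutes". For controls, "They underwent no other intervention during the NST procedure", and no duration is given. Both paragraphs end alike: "After the procedure was completed, the Prenatal Comfort Scale, Vital Signs Form and State Anxiety Scale were administered again".

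Under *Data Collection Tools* the Vital Signs Form is described in one sentence: "The form was used to record the pregnant women's body temperature, pulse rate, respiration rate and blood pressure values". Posture, rest before the reading and time of reading are not mentioned.

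The *Statistical Analysis of the Data* section names two tests that could address vital signs. The Wilcoxon test "was used to test the difference in the dependent groups at two different measurement times". For data that are not normally distributed, "the Mann-Whitney U test was used to evaluate the difference between two groups". The section does not say which of the two answers the vital-signs question, or whether the between-group test is applied to after values or to changes.

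**The concern.** Vital signs are one of the three outcomes in the title and aim. The before reading precedes the instruction to lie down, and the after reading follows the NST. Between the two, a woman in either arm has lain on her side, rested, let time pass and finished the test. Pulse, respiration and blood pressure could move for any of these reasons.

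A within-arm test asks whether the average change is zero. It cannot separate music from the rest of the session. If the report relies on it, a significant fall in the music arm could be read as a music effect when controls fell by the same amount. A related trap is to set the two within-arm p-values side by side and read significance in one arm only as a difference between arms. That pattern is not a test of the difference and arises often when the true changes are equal.

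**Working it through.** The plan gives no figure on this point. Its only calculation, the minimum of 70 women, concerns anxiety and does not bear on vital signs.

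**Inputs from the documents.** Music arm n = 93, control arm n = 80, significance level 0.05. The Wilcoxon test is read as run within each arm.

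**Assumed inputs (not in the documents).** No music effect; a shift common to both arms of 2, 3 or 5 mmHg; SD of the within-woman change 8 or 10 mmHg; normal changes; two-sided tests.

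**Step 1: power of the within-arm test.** With a Wilcoxon efficiency of 0.955 relative to the paired t-test, the effective n is 0.955 × 93 = 88.8 (music) and 0.955 × 80 = 76.4 (control). The noncentrality is (shift / SD) × √(effective n), and power comes from the noncentral t distribution. For example, 3 mmHg with SD 8 in the music arm gives 3/8 × √88.8 = 3.53 and power 93.8%.

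| Shift | SD | Music arm significant | Control arm significant |
|---|---|---|---|
| 2 mmHg | 8 | 64.4% | 57.8% |
| 2 mmHg | 10 | 46.2% | 40.8% |
| 3 mmHg | 8 | 93.8% | 89.9% |
| 3 mmHg | 10 | 79.8% | 73.5% |
| 5 mmHg | 8 or 10 | over 99% | 99% or more |

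**Step 2: significant in music only.** The arms are independent, so the probability is P(music) × [1 − P(control)].

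- 2 mmHg, SD 8: 0.644 × 0.422 = 0.27
- 2 mmHg, SD 10: 0.462 × 0.592 = 0.27
- 3 mmHg, SD 8: 0.938 × 0.101 = 0.09
- 3 mmHg, SD 10: 0.798 × 0.265 = 0.21
- 5 mmHg: under 0.01, because both arms are nearly always significant

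**Step 3: how much is due to unequal arms.** With 173/2 = 86.5 women per arm and a 2 mmHg shift, power is 61.2% (SD 8) or 43.5% (SD 10). Significant in music only then has probability 0.612 × 0.388 = 0.24 or 0.435 × 0.565 = 0.25. The imbalance adds about 3 percentage points. With 93 and 80, significant in control only has probability 0.578 × 0.356 = 0.21 or 0.408 × 0.538 = 0.22.

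**Step 4: the between-arm test.** In 4,000 simulated trials per setting, with 93 and 80 women, no music effect and a common shift of 0 to 0.5 SD of change, Mann-Whitney on change was significant in 4-6% at every shift. The music-arm Wilcoxon was significant in 5% at no shift, 47% at 0.2 SD, 79% at 0.3 SD and 99.6% at 0.5 SD. The 0.2 SD shift (2 mmHg with SD 10) gave significance in music only in about 29%, close to the 27% from the formula.

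**The case against.** The strongest reply is that the design already deals with a shared shift. Allocation is randomized, both arms follow the same measurement order and positioning instruction, and a between-group test is planned. Step 4 bears this out: a between-arm test on change keeps its error rate near 5%. The plan nowhere says that the Wilcoxon test will establish the music effect. All of this stands. It narrows the point to the within-arm test and to the plan's silence on which test decides.

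Four stronger readings are tempting, and the documents do not support them.

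- *That the before reading is upright and the after reading lying.* The order of the text suggests that the first precedes lying down, but posture is not stated at either reading. A woman could have been sitting for both, which would leave rest and elapsed time but little posture difference.
- *That every woman lay for 20-30 minutes.* That figure is the music arm's listening time. The control duration is not given.
- *That the unequal arms produce the misleading pattern.* Equal arms already give 24-25%.
- *That the randomized comparison is biased.* Nothing shows this. It would be affected only if the session differed between arms in some way besides music, such as NST duration, and the documents are silent on that.

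It can also be said that a within-arm test absorbs time effects for comfort and anxiety as well. That is true. Vital signs are the clearest case, because the positioning instruction falls between the two readings.

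**Conclusion.** The concern holds in a limited form and is minor. The within-arm Wilcoxon test combines any music effect with rest, elapsed time and possibly posture, so by itself it cannot show that music changed vital signs. The plan does include a between-group test, but does not say that this test uses the before values or decides the question.

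The size depends on a shift and an SD that the documents do not give, and even the direction of any posture effect is unknown. The 27% for significance in music only (2 mmHg) and the 80-94% for a significant music arm (3 mmHg) come from different scenarios and should not be combined. As the shift grows, both arms become significant and the music-only pattern fades, but the music-arm p-value still says nothing specific about music.

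A reader might infer that the trial cannot answer its vital-signs question. It can, through the randomized comparison, provided the arms differed only in music.

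**What to change.** In *Statistical Analysis of the Data*, state that conclusions on each vital sign rest on the between-arm difference in after values adjusted for the before value, by ANCOVA or a rank-based equivalent, with a 95% confidence interval. Present within-arm changes descriptively, without p-values.

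In *Data collection*, report what is known of posture and timing at both readings, and give the NST duration by arm. If durations differed, say so beside the between-arm result, because adjustment for the before value does not remove that difference.

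The study is described in the past tense with 93 and 80 women, so standardizing the readings now would come too late. The analysis change uses data already collected and costs a few sentences and one model per vital sign. Reporting posture, timing and duration costs little if they were recorded; otherwise, state that they were not.
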